Schedule of treatment and specimen collection:	
All patients will be scheduled to take deferiprone daily, 2 times a day, for up to 18 months.
 
Safety and efficacy assessments will be conducted at the following time points:
 
 • Hematology: Weekly up to Visit 4 (End of Study) or early termination • Blood chemistry: Visits 1, 2, 3, and 4 or early termination • ECG: Visits 1 and 4 or early termination • BAD: Visits 1, 2, 3, and 4 or early termination • PGI-I: Visits 2, 3, and 4 or early termination * 
* The PGI-I will be conducted at Visit 1 as well, but its data on that day will be applicable only to the initial study (for which this is the last visit), not to the extension study.
	
Statistical methods:	
Safety Analysis
 
The incidences of AEs and SAEs reported during deferiprone therapy for all patients, from the start of TIRCON2012V1 to the completion of TIRCON2012V1-EXT, will be tabulated. Similar tables will be produced for the severity of AEs and for their relationship to the study medication. Time to onset and duration of all AEs with an incidence of >5%, and of any AEs of special interest (e.g., worsening of dystonia), will be summarized with descriptive statistics.
 
The percentage of discontinuations due to AEs will be calculated, and the AEs leading to discontinuation will be summarized in a frequency table by preferred term.
 
Laboratory data (hematology and blood chemistry) will be summarized using descriptive statistics for continuous variables and frequency tables for discrete variables. The incidences of out-of-range data will be tabulated, and the changes from baseline to the end of study will be examined using shift tables.
 
Efficacy Analysis
 
For the efficacy measures of BAD (total score and by body region) and PGI-I, the change from baseline to each of the measurement time points will be determined and summarized using descriptive statistics. A paired t-test will be used to assess the statistical significance of the changes in these efficacy outcomes from baseline to Visit 4. For the BAD total score and for PGI-I, the proportions of patients determined to be responders at Visit 4 will be calculated and presented along with 95% confidence intervals.
	

Name of Sponsor: ApoPharma Inc.	Individual Study Table Referring to Part of the Dossier Volume: Page:	(For National Authority Use Only)
Name of Finished Product: Deferiprone		

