- Remind the patient/authorized legal representative to do the following:
 - Return all study medication containers at the next visit, whether empty or unused
 - Keep careful track of adverse events and medication(s) used
 - Interrupt therapy immediately in the event of fever (temperature ≥ 38.5 °C/101.3 °F), and promptly report any symptoms indicative of infection such as fever or flu-like symptoms
 - If patient is on a regular dosing regimen of any of the medications listed in [Appendix 3](#) or of any other medication that has the potential to affect dystonia symptoms, to stay on the same regimen for the duration of the study. Any change in dose and dosing regimen should be limited to circumstances judged as absolutely necessary by the investigator.
 - If patient is being treated with any such medications on a PRN basis, to use them only under circumstances judged as absolutely necessary by the investigator, and to interrupt treatment prior to the next study visit according to the following timelines:

Medication	Treatment interruption period prior to current visit
Baclofen	30 days
Trihexyphenidyl	30 days
Clonazepam	30 days
Tizanidine	30 days
Botox	60 days
Tetrabenazine	90 days

- If patient has a DBS system or Baclofen pump in place, to make every effort to maintain the same DBS stimulation parameters or Baclofen pump settings for the duration of the study. Any changes in settings should be limited to circumstances judged as absolutely necessary by the investigator.
- If leaving the study before completion, to return to the clinic for an Early Termination Visit as soon as possible and no later than 30 days following the last dose of study medication
- Provide patient with card containing contact information for emergency services, and advise that this card should be carried at all times
- Schedule next study visit

Weekly Blood Draws (every 7 ± 3 days)

Note: These blood draws can be conducted either at a local laboratory or at the study site.

- Collect blood sample for hematology assessment. The results are to be reviewed by the investigator in a timely manner when they are received from the laboratory.

Telephone Contact (Week 1 ±2 days and Week 2 ±2 days)

A study staff member will contact the patient and/or legal representative by telephone at Week 1 and Week 2 with the following queries and reminders, and will document the responses:

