 - If patient has been taking any of these medications on a PRN basis since the start of study TIRCON2012V1, verify that treatment was interrupted prior to the current visit according to the following timelines:

Medication	Treatment interruption period prior to current visit
Baclofen	30 days
Trihexyphenidyl	30 days
Clonazepam	30 days
Tizanidine	30 days
Botox	60 days
Tetrabenazine	90 days

- Collect blood samples for the following assessments:
 - Hematology
 - Blood chemistry
 - Pregnancy testing for all sexually active females of childbearing potential (if applicable; in cases where the investigator determines there is no reasonable risk of pregnancy because of significant incapacity, pregnancy testing will not be performed)
- Collect a urine sample for urinalysis
- Measure vital signs, weight, and height
- Perform a 12-lead ECG

- Conduct contraceptive counseling for sexually active patients
- The following must be performed by a qualified investigator or a qualified delegate:
 - Conduct a physical examination
 - Record administration of the BAD in a standardized manner on videotape, and transmit tape to the evaluation center
 - Administer the Patient Global Impression of Improvement
- Collect any empty containers or unused medication from the previous 6 months, and perform drug accountability
- Instruct the patient/authorized legal representative to report any AEs that occur in the next 14 days and any SAEs that occur in the next 30 days

Any ongoing AE or SAE is to be followed until one of the following outcomes:

- AE/SAE is resolved
- Patient's condition stabilizes
- AE/SAE is otherwise explained
- Patient is lost to follow-up

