7.2.2 Laboratory Measurements

Samples for laboratory safety assessments will be taken at the time points indicated below. If a patient withdraws from the study, the End of Study procedures are to be performed at an early termination visit.

Hematology: Complete blood count (CBC), including total WBC, ANC, platelet count, and hemoglobin	Weekly
Blood chemistry: Serum ferritin, total protein, GGT, LDH, sodium, potassium, chloride, glucose, total, bilirubin, AST, ALT, albumin, blood urea nitrogen, calcium, creatinine, uric acid, alkaline phosphatase, and amylase	Visits 1, 2, 3, and 4
Urinalysis: pH, specific gravity, glucose, protein, ketones, and blood. If indicated by the dipstick, sediment microscopy will be performed.	Visits 1, 2, 3, and 4
Pregnancy testing: Serum pregnancy tests will be performed for all sexually active females of childbearing potential (unless the investigator determines there is no reasonable risk of pregnancy because of significant incapacity)	Visits 1, 2, 3, and 4

The investigator must review and interpret each laboratory report, and document the review by signing or initialing and dating the report. Any laboratory values that fall outside a clinically accepted range, or values that differ significantly from previous values, must be marked by the investigator as either “CS” (clinically significant) or “NCS” (not clinically significant). Any that are marked as CS must be further explained and documented as an AE.

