9 STATISTICAL ANALYSIS

9.1 Endpoints

9.1.1 Primary Endpoints

- Adverse events (AEs): Frequency, severity, time to onset, duration, and relatedness to study product

- Serious adverse events (SAEs): Frequency, severity, time to onset, duration, and relatedness to study product
- Number of discontinuations due to AEs
- Hematology assessments
- Blood chemistry assessments
- ECG assessments

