4.4 Safety Analyses

The safety endpoints include:

- Adverse events (AEs): Frequency, severity, time to onset, duration, and relatedness to study product
- Serious adverse events (SAEs): Frequency, severity, time to onset, duration, and relatedness to study product

-
- Number of discontinuations due to AEs
 - Hematology assessments
 - Blood chemistry assessments
 - ECG assessments

All safety data collected will be presented in listings and summary tables or graphs to give an overview of the safety findings. All safety endpoints will be analyzed based on the safety population. For patients continuing on deferiprone in the extension study, this time period will be from the start of TIRCON2012V1 to the completion of TIRCON2012V1-EXT; for those who received placebo in the initial study and are switching to deferiprone in the extension study, it will be from the start to the completion of the extension study.

For those patients who do not follow the scheduled time window exactly for each visit or withdraw from the study early, the following time window will be employed to classify the safety data into each scheduled visit according to the time elapsed from the first medication date (date of exposure) to the assessment date:

Month 1.5 visit: 0.75 to <2.25 months

Month 3 visit: 2.25 to <4.5 months

Month 6 visit: 4.5 to <9 months

Month 12 visit: 9 to <15 months

Month 18 visit: 15 to <21 months

Month 24 visit: 21 to <27 months

Month 30 visit: 27 to <33 months

Month 36 visit: 33 to <39 months

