Height n Mean (SD) Median (Min, Max)	Baseline	xx xx.xx (xx.x) xx.x (xx.x, xx.x)
	Month 12	xx xx.xx (xx.x) xx.x (xx.x, xx.x)
	Month 18	xx xx.xx (xx.x) xx.x (xx.x, xx.x)
	Month 36	xx xx.xx (xx.x) xx.x (xx.x, xx.x)

Table 14.3.4.1 Summary of 12-lead ECG parameters at each visit – safety population

Test	Visit	DFP (N=xx)
Heart Rate (bpm) n Mean (SD) Median (Min, Max)	Baseline	xx xx.xx (xx.x) xx.x (xx.x, xx.x)
	Month 18	xx xx.xx (xx.x) xx.x (xx.x, xx.x)
	Month 36	xx xx.xx (xx.x) xx.x (xx.x, xx.x)
Repeat for PR Interval, QRS Interval, QT Interval, QTcB Interval, and QTcF Interval

Table 14.3.4.2 Proportions of normal and abnormal ECG results in each visit – safety population

Test	Visit	DFP (N=xx)
ECG n Abnormal (n (%)) Normal (n (%))	Baseline	xx
		xx (xx)
		xx (xx)
	Month 18	xx
		xx (xx)
		xx (xx)
Month 36	xx	
	xx (xx)	
	xx (xx)	

Table 14.3.5.1 Treatment compliance (%) by visit – safety population

Parameter	Visit	DFP (N=xx)
Compliance (%) n Mean (SD) Median (Min, Max)	Month 1.5	xx xx.xx (xx.x) xx.x (xx.x, xx.x)
	Month 3	xx xx.xx (xx.x) xx.x (xx.x, xx.x)
	Month 6	xx xx.xx (xx.x) xx.x (xx.x, xx.x)
	Month 12	xx xx.xx (xx.x) xx.x (xx.x, xx.x)
	Month 18	xx xx.xx (xx.x) xx.x (xx.x, xx.x)
	Month 24	xx xx.xx (xx.x) xx.x (xx.x, xx.x)
	Month 30	xx xx.xx (xx.x) xx.x (xx.x, xx.x)

	Month 36	xx xx.xx (xx.x) xx.x (xx.x, xx.x)
--	----------	--

Table 14.3.6.1 Concomitant Medications – safety population

	DFP
	Exposure (subject-years): x.xx
	Total Subjects Exposed: xx
	Total Subjects Reporting: xx
Preferred Name	N Subjects (%)
Ccccc	x (x.x)
Ccccc	x (x.x)
.....	x (x.x)

Table 14.3.6.2 Rescue Medications – safety population

	DFP
	Exposure (subject-years): x.xx
	Total Subjects Exposed: xx
	Total Subjects Reporting: xx
Preferred Name	N Subjects (%)
Baclofen	x (x.x)
Diazepam	x (x.x)
.....	x (x.x)

Table 14.3.6.3 PRN Medications – safety population

	DFP
	Exposure (subject-years): x.xx
	Total Subjects Exposed: xx
	Total Subjects Reporting: xx
Preferred Name	N Subjects (%)
Botulinum toxin type A	x (x.x)
Baclofen	x (x.x)
Clonazepam	x (x.x)
.....	x (x.x)

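### Many early-termination ECGs have no row in the SAP's ECG tables and no listing, so readings not flagged clinically significant have no planned output

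*SAP*

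**What the plan says.** **Collection.** The protocol synopsis schedules "ECG: Visits 1 and 4 or early termination". Table 5.1 agrees, and Protocol 5.1 gives the instruction "Perform a 12-lead ECG" under the combined Visit 4 / Early Termination Visit. Protocol 7.2.3.3 names only Visits 1 and 4, but 7.2.2 adds for withdrawals: "If a patient withdraws from the study, the End of Study procedures are to be performed at an early termination visit". The early-termination (ET) visit is to take place "no later than 30 days following the last dose of study medication" (Protocol 5.1).

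**Status.** Protocol 9.1.1 lists "ECG assessments" among the primary endpoints, and SAP 4.4 repeats this among the safety endpoints.

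**Classification.** For patients who are off schedule or withdraw early, SAP 4.4 states that "the following time window will be employed to classify the safety data into each scheduled visit". The visits are Months 1.5, 3, 6, 12, 18, 24, 30 and 36. Under SAP 3.5 the clock starts at the first dose in the initial study for patients already on deferiprone (DFP-DFP, here continuers) and at the first extension dose for former placebo patients (Placebo-DFP, here switchers).

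**Output.** SAP 4.4 promises: "All safety data collected will be presented in listings and summary tables or graphs". In SAP section 7, Table 14.3.4.1 ("Summary of 12-lead ECG parameters at each visit") and Table 14.3.4.2 (normal/abnormal) have rows for Baseline, Month 18 and Month 36 only. The listing index in SAP section 6 covers vital signs, height and weight, urinalysis, pregnancy tests, telephone contacts and bottle numbers, but not ECG.

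**The concern.** Each extension patient has one scheduled ECG after Visit 1, taken at Visit 4 or at early termination. For a switcher who withdraws before month 15, the ET reading is the only scheduled ECG on deferiprone, and that patient would be seen only in the Baseline row. The patients affected include those who stop for adverse events. If the shells are followed as drawn, the PR, QRS, QT and QTc summaries and the normal/abnormal proportions lean toward completers. A QTc shift in a withdrawn patient that nobody flagged as clinically significant would be in the database but in no table, figure or listing.

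ECG is also handled differently from comparable data. Hematology, biochemistry, urinalysis, vital signs and weight have a row for every safety window.

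**Working it through.** The documents state no figure for this point, so there is none to reproduce. The check maps the time of an ET ECG onto the SAP's windows.

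**Inputs**
- Windows with an ECG row after baseline (SAP 4.4): Month 18 = 15 to <21 months; Month 36 = 33 to <39 months.
- Clock (SAP 3.5): the extension covers about months 18 to 36 for continuers and months 0 to 18 for switchers.
- Group sizes (SAP 3.2): 44 continuers and 24 switchers, 68 in all.
- Safety data are analysed as observed cases without imputation (SAP 3.5), so no other rule moves an ET reading into a row.

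**Where an ET ECG lands**

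| Group | Time since first dose | Assigned visit | ECG row? |
|---|---|---|---|
| Continuer | 18 to <21 months | Month 18 | yes |
| Continuer | 21 to <33 months | Month 24 or 30 | no |
| Continuer | 33 to <39 months | Month 36 | yes |
| Switcher | before 0.75 months | none | no |
| Switcher | 0.75 to <15 months | Month 1.5, 3, 6 or 12 | no |
| Switcher | 15 to <21 months | Month 18 | yes |

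**Uniform withdrawal over 18 months, ECG at the last dose**
- Continuers: (33 − 21)/18 = 12/18 = 67% without a row.
- Switchers: 15/18 = 83% without a row.
- Weighted 44:24, assuming equal withdrawal rates: (44 × 12 + 24 × 15)/(68 × 18) = 888/1224 = 72.5%, about 73%.

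**Front-loaded withdrawal.** Take the density of withdrawal time u as proportional to exp(−λu) on 0 to 18 months, with λ = ln 2/h. The share between a and b is (exp(−λa) − exp(−λb))/(1 − exp(−18λ)). The half-life h was set to 9, 6 or 3 months and the ET visit to 0, 0.5 or 1 month after the last dose.
- Lowest weighted result (h = 3, no delay). Continuers, u from 3 to 15: (0.5 − 0.03125)/0.984375 = 0.476. Switchers, u from 0 to 15: (1 − 0.03125)/0.984375 = 0.984. Weighted: (44 × 0.476 + 24 × 0.984)/68 = 0.655.
- Highest weighted result (h = 6, delay 1 month). Continuers 0.680, switchers 0.916. Weighted: (44 × 0.680 + 24 × 0.916)/68 = 0.764.
- The range over these scenarios is 66% to 76%. Uniform timing with the same delays gives 71% to 73%.

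**Limiting cases**
- All ET ECGs in the first 3 months of the extension: only the switchers' lack a row, 24/68 = 35%.
- All between months 3 and 15: 100%.
- All from month 15 onward: 0%, because both groups then fall in a window with a row.

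**A further gap.** A continuer's ET ECG at 18 to <21 months shares the Month 18 window with the same patient's Visit 1 ECG. The SAP gives an averaging rule for efficacy outcomes (section 4) and laboratory tests (4.4.2), but none for ECG.

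**The case against.** A reader might infer that withdrawal ECGs appear nowhere, or that the SAP decided to leave them out. The documents do not support that.
- A clinically significant ECG abnormality that is not part of an event already recorded is an adverse event (Protocol 7.2.1.1), and SAP 4.4.4 says such abnormalities will be reported. These findings reach the adverse event tables and listings.
- Withdrawals due to adverse events get their own listing and narratives (SAP 4.4.1).
- SAP 4.4 commits to listing all safety data, section 7 lets the final tables differ from the shells, and sections 5 and 6 allow for added tables and listings. The gap is a mismatch between the SAP's text and its planned outputs.

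The permission to vary the shells does not close the gap, however. Nothing says that ET ECGs go into the Month 18 or Month 36 rows regardless of timing, and putting them there would contradict the 4.4 windows.

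A reader might also take the missing change-from-baseline and shift tables as a departure from plan. They are not: shift tables are specified for laboratory data only, and for ECG the protocol's analysis section promises clinically significant abnormalities and normal/abnormal counts. Nor is it an error that the Month 18 row combines continuers and switchers, since the SAP counts time from first deferiprone dose by design.

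Two objections stand in full. The percentages depend on withdrawal timing that the documents do not give, and they apply to an unknown, possibly small, number of ET ECGs. And a row built from each patient's last available ECG would carry a continuer's Visit 1 reading forward when no ET ECG was taken, against the observed-case rule in SAP 3.5.

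**Conclusion.** The point holds for ET readings and normal/abnormal results not flagged clinically significant. Followed as written, the SAP gives them no planned output when they fall before month 15 in switchers or at total months 21 to <33 in continuers. That follows from the windows, the shells and the listing index alone.

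The size is conditional. About 73% of ET ECGs lack a row if withdrawal is uniform and equally frequent in both groups, and 66% to 76% under the front-loaded scenarios. The share is 35% if all fall in the first 3 months, and lower still if withdrawals cluster in the last 3. That a majority is affected is a reasonable expectation, not a fact in the documents.

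The study is single-arm and its ECG analysis is descriptive, so no hypothesis test is at risk. What suffers is the completeness of a primary safety endpoint in the patients who stopped early. The plan should be corrected.

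**What to change.** 1. Add to Tables 14.3.4.1 and 14.3.4.2 an end-of-study row (Visit 4 or early termination), shown for Placebo-DFP and DFP-DFP. Use only the ECG taken at Visit 4 or the ET visit of the extension, and never carry Visit 1 forward. Adding rows for the existing windows instead would still miss a switcher's ECG before 0.75 months.
2. Add an ECG listing under 16.2.9 with the days since last dose, because the ET visit may fall up to 30 days after it.
3. State which reading the Month 18 row uses when a continuer has both a Visit 1 and an ET ECG in that window.

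Change-from-baseline and shift panels are optional.

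The main cost is one extra row in each table and one listing, from data already collected. With these, the share of ET ECGs without a planned output falls to 0% whatever the withdrawal timing. The drawback is that the new row pools different exposure durations and some off-drug readings, which a footnote should state.
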